9.1. Recruitment

Patients will be identified by clinicians working in pleural services in the selected centres, from any part of the pleural service (inpatient, outpatient, day case). Patients identified as being eligible for enrolment will be approached by the clinical team responsible for their care (most likely to be the respiratory or pleural team) and provided with written information about the study.

9.2. Screening and Eligibility Assessment

Patients will be screened for eligibility from pleural procedure lists and pleural clinics. Any patient meeting the inclusion criteria will be approached for the study by the clinical team who will then contact the research team if a potential participant is interested in taking part.

Radiology (CXRs) taken as part of routine clinical care be used to screen for eligibility by confirming the presence of a pleural effusion. If no CXR is available, ultrasound may be used to screen (i.e. CXR is not a requirement for entry to the study). In all cases, ultrasound should be performed **before randomisation** (as part of routine clinical care) to ensure there is sufficient fluid to conduct a therapeutic intervention including indwelling pleural catheter.

Patients who decline participation in the study will have the reason for non-participation (if volunteered) in the trial recorded on the screening logs.

9.3. Informed Consent

Patients will be judged to have capacity to consent to the trial if they:

- Understand the purpose and nature of the trial.
- Understand what the trial involves, its benefits, risks and burdens.
- Understand the alternatives to taking part.
- Retain the information long enough to make an effective decision.
- Make a free choice.
- Make this particular decision at the time it needs to be made (though their capacity may fluctuate, and they may be capable of making some decisions but not others depending on their complexity).

The Participant Information Sheet (PIS) and Consent Form will be presented and explained to the participants detailing the exact nature of the study; what it will involve for the participant; the implications and constraints of the protocol; any known adverse effects and any risks involved in taking part. It will be clearly stated that the participant is free to withdraw from the study at any time for any reason, without their future care being affected, and with no obligation to give the reason for withdrawal. The PIS will also include information about optional interviews for patients.

Participation in the study will be discussed with the patient at the appropriate outpatient appointment or inpatient consultation, which will form part of their normal care pathway. Patients will be given

sufficient time, as determined by the patient, to consider study entry and the opportunity to question the researcher, their GP or other independent parties to decide whether they will participate in the study. Written informed consent will then be obtained by means of participant dated signature and dated signature of a member of the research team. Due to the nature of the clinical presentation (i.e.. significant breathlessness requiring intervention), *recruitment can occur* from 2 weeks prior to first procedure up to and including the day of procedure as long as the patient has had sufficient time to consider their participation and provide meaningful consent.

As part of routine clinical discussions, participants with potential MPE undergoing pleural biopsy and IPC will be aware that there is a significant concern that their effusion is caused by an underlying cancer, with pleural biopsies required to confirm the diagnosis. All patients will need to consent to study inclusion prior to their first pleural procedure. This information will be included in the PIS. If clinical discussions about likely malignancy cause the patient to become distressed, the treating clinician may choose not to give further information about the STREAMLINE trial. In this situation the patient's details should be recorded on the screening log with reason for non-enrolment included.

Patients Declining to participate in STREAMLINE

Patients offered, but declining participation in the STREAMLINE study will be asked if they would be willing to participate in qualitative interviews so we can also gain information on the reasons for their non-participation. Consent for interviews will be undertaken via a separate consent form.

9.4. Randomisation

Once the participant has given written consent to the study, a member of the trial team, authorised and trained will randomise the participant to a treatment allocation. Consent can be given for randomisation up to 2 weeks before the randomisation event (with ongoing consent confirmed verbally with the patient).

In all cases, randomisation can occur on the day of procedure, or up to 1 week in advance to allow for planning of procedure lists.

Randomisation will occur 1:1 between the standard pathway and the accelerated pathway, and performed by sites using a web-based randomisation system, (Sealed Envelope - https://www.sealedenvelope.com/). Minimisation with a residual randomised component will occur with the following minimisation criteria:

- Known extrapleural malignancy or not
- Clinical suspicion of mesothelioma or not

9.5. Blinding and code-breaking

The trial will be unblinded due to the nature of interventions, so no un-blinding procedures are required.

9.6. Description of study intervention(s), comparators and study procedures (clinical)

There are no investigational medicinal products in this trial with all interventions being standard medical practice. The interventions are described in the sections above with standard operating procedures for the interventions as part of this study.

Standard pathway: Patients will receive a therapeutic pleural aspiration as the first procedure as part of the 'standard care' pathway, and can receive thoracoscopic pleural biopsies, image guided pleural biopsies and IPC after the first intervention as determined by the clinical team.

Accelerated pathway: Patients in the accelerated arm will receive pleural biopsies (via either thoracoscopy or image guided) AND IPC as the first intervention. Further IPC management (frequency of drainage, use of talc via the IPC, IPC removal) will be at the discretion of the local investigator according to clinical need, and guided by a trial specific procedure (TSP).

Concomitant medication

All concomitant medications are permitted in this trial. Use of medications which are thought to reduce pleurodesis success (such as steroids) are permitted but will be recorded on CRFs. Talc for pleurodesis may be used as part of the standard care pathway and after the trial intervention in the accelerated pathway, as guided by a separate TSP.

9.7. Baseline Assessments

A baseline assessment will be performed by a member of the trials team and documented on the relevant CRF. Baseline data may be collected and entered onto the CRF up to 2 weeks prior to the planned trial procedure date. Baseline data will include:

- Confirmation of inclusion / exclusion criteria
- Participant demographics
- Relevant medical history including:
 - WHO performance status
 - \circ $\;$ Duration of symptoms at the point of recruitment
 - Type of malignancy (if a known history of malignancy)
 - Pleural interventions on ipsilateral side to date
 - Asbestos exposure history
- Radiology results from scans done as part of routine care (labelled 'routine' in schedule of procedures)
- Pre-procedure breathlessness and chest pain VAS -
- Pre-procedure quality of life assessments and HADS score
- Results of routine clinical blood tests from any time within 4 weeks pre-randomisation

Demographic data, medical history and baseline parameters for breathlessness, pain and quality of life/anxiety will be collected directly pre and post the first intervention. Recording of these parameters will continue on a 3 times per week basis for 6 weeks post initial intervention. Given the demographic of patients expected in the STREAMLINE study, participant facing forms (such as visual analogue scores and questionnaires) will be printed as part of a paper diary to complete at home after the first procedure. Clinician completed CRFs will be entered directly into electronic database. In depth qualitative interviews assessing patient acceptability and experience will be undertaken at or after the 6 week follow up.

Patients will then undergo the index procedure as dictated by randomisation – either pleural aspiration (standard pathway) or pleural biopsy + IPC (accelerated pathway)

- Oxford participants may also be approached and separately consented to gift pleural fluid samples to the Oxford Radcliffe Biobank.
- Following discharge patients will complete weekly VAS dyspnoea scores 3 times per week for 6 weeks and weekly quality of life scores via a paper diary.

Clinical Research Protocol Template version 15.0 CONFIDENTIAL © Copyright: The University of Oxford and Oxford University Hospitals NHS Foundation Trust 2019 Page 24 of 38

9.8. Subsequent Visits

The follow up period is 12 weeks post procedure Trial follow up appointments will take place at

- 2 weeks ± 3 days
- 6 weeks ± 5 days and
- 12 weeks ± 7 days post procedure

This follow up schedule mirrors normal clinical care. Appointments should take place at the patient's local centre.

Data collected at each follow up will be:

1. VAS diary (week 2, 6 visit)

2. QLQ C30, EQ 5D 5L, and HADS diary (week 2, 6 visit)

3. Side effects attributable to the trial intervention

4. Information on healthcare utilisation including inpatient and outpatient admissions for pleural effusion management and any other cause

5. Ultrasound and Chest X Ray will be conducted at 2 weeks and 6 weeks as part of standard care, and results documented on the CRF.

At each follow up visit participants will undergo a standard clinical consultation, which should be conducted by a medical member of the trials team and the appropriate CRF should be completed. A chest x-ray (and ultrasound if available) should be performed (as per routine clinical care) and the results entered into the CRF. Participant completed diaries will be reviewed at these visits.

Participants will be asked to complete a home VAS diary three times per week and Quality of Life scores (1 per week) for 6 weeks post index procedure.

In light of the COVID-19 pandemic it is possible that participants and/or sites will judge that participant contact should be minimised. In recognition of this, follow up visits at 12 weeks may be carried out remotely via telephone.

Reasonable travel expenses to participants for visits that do not align with clinical care will be covered as part of the per participant costs. All feasible efforts have been made to align clinical and study visits, however, 'non-aligned' visits may occur in cases, for example whereby participants have required clinical review outside the study visits and thus are required to attend for a study visit sooner than otherwise required.

Visual Analogue Scale (VAS) scoring

VAS outcomes will be captured using participant paper diaries. Following hospital discharge, participants will receive a trial nurse phone call once per week, according to local availability, as a reminder to complete the VAS scores. The schedule of VAS scores is as follows:

• Pre-procedure VAS (day of first procedure, immediately prior).

- Post procedure VAS (day of the procedure, before discharge)
- Then thrice weekly for 6 weeks (participants will be advised to conduct this at a similar time each day to their convenience, on specified days, e.g. Monday / Wednesday / Friday).

Qualitative Interviews

Participants (consenting to be interviewed) will be approached for participation in qualitative interviews regarding their experiences during the study or their reasons for refusing inclusion/randomisation. This will aim to establish priorities of care and therefore important outcomes in the planned multicentre randomised controlled trial. It is anticipated that the interviews will take place at a scheduled follow up visit. The interviews will be undertaken by members of the research team trained in qualitative methodology.

9.9. Sample Handling

Samples for routine clinical care will be conducted as per local hospital practice. They do not play a part in the study or analysis.

Oxford participants may be approached separately to consent to have their pleural fluid removed as part of the procedure processed and stored as part of the Oxford Radcliffe Biobank.

9.10. Early Discontinuation/Withdrawal of Participants

During the course of the study a participant may choose to withdraw early from the study treatment at any time without having to give a reason and this will not affect their future care. This may happen for several reasons, including but not limited to:

- The occurrence of what the participant perceives as an intolerable AE.
- Inability to comply with study procedures
- Participant decision

Participants may choose to stop treatment and/or study assessments but may remain on study follow-up.

Participants may withdraw their consent, meaning that they wish to withdraw from the study completely.

9.11. Definition of End of Study

The end of study declaration will occur at the time of final database lock.

10. SAFETY REPORTING

10.1. Definition of Serious Adverse Events

A serious adverse event is any untoward medical occurrence that:

- results in death
- is life-threatening
- requires inpatient hospitalisation or prolongation of existing hospitalisation
- results in persistent or significant disability/incapacity
- consists of a congenital anomaly or birth defect.

Other 'important medical events' may also be considered a serious adverse event when, based upon appropriate medical judgement, the event may jeopardise the participant and may require medical or surgical intervention to prevent one of the outcomes listed above.

NOTE: The term "life-threatening" in the definition of "serious" refers to an event in which the participant was at risk of death at the time of the event; it does not refer to an event which hypothetically might have caused death if it were more severe.

10.2. Reporting procedures for AEs

The population of patients involved in STREAMLINE is one in which a high number of adverse events are expected due to the underlying likely disease (metastatic cancer), therefore only adverse events meeting the criteria to be a Serious Adverse Event will be recorded.

10.3. Reporting Procedures for Serious Adverse Events

Table of Anticipated Events

Given the comorbid nature of the patient population, the below table lists events that are anticipated in this population that do not require expedited reporting but will be captured in CRFs. Many of these will not be causally related to the investigational intervention, but rather will be a direct consequence of the patient's underlying malignancy. Other events may occur as a result of a trial-related intervention but are well-documented and regarded as normal complications of IPC use, thoracoscopy or pleural aspiration.

Relating to pleural intervention	Pain requiring analgesia
(aspiration, IPC, biopsy)	Hypotension
	Respiratory failure
	Fever
	Atrial fibrillation
	Haemorrhage
	Organ damage
	Postoperative pneumothorax or air leak
	Bronchopleural fistula
	Pneumonia
	Hospital admission
	Empyema
	Subcutaneous emphysema
	Failure to reach a diagnosis
	Operative skin site infection
	Port site tumour growth

CONFIDENTIAL

Clinical Research Protocol Template version 15.0

© Copyright: The University of Oxford and Oxford University Hospitals NHS Foundation Trust 2019 Page 27 of 38

	Organ damage				
	Respiratory failure				
	Pleural infection				
	IPC blockage				
	Failure of IPC requiring replacement				
	Catheter tract metastasis				
Relating to underlying	derlying Death related to underlying malignancy				
malignancy	Recurrent pleural fluid				
	Surgery or procedure related to underlying malignancy or				
	pleural fluid recurrence				
	Malignancy treatment related side effects (including				
	chemotherapy and radiotherapy side effects e.g. neutropaenic				
	sepsis)				

The **safety reporting period** is for **6 weeks post initial procedure**, or **until IPC removal** (if removed prior to 6 weeks – i.e. whichever is sooner).

SAEs that are considered (by the site investigator) to be **possibly, probably or definitely related** to the study intervention (i.e. the procedure conducted for the study) **and not an anticipated event** (Appendix A) will be reported on the relevant reporting form (PM124-A Serious Adverse Event Report Form (non-CTIMPs)) and emailed to ORTU without delay. ORTU will perform an initial check of the report, request any additional information, ensure it is reviewed by a nominated Medical Reviewer.

Any anticipated SAE or SAE considered **not related** to the study intervention by the local investigator does not require expedited reporting but will be recorded on the appropriate procedure, discharge or follow up CRF.

A serious adverse event (SAE) occurring to a participant should be reported to the REC that gave a favourable opinion of the study where in the opinion of the Chief Investigator the event was 'related' (resulted from administration of any of the research procedures) and 'unexpected' in relation to those procedures. Reports of related and unexpected SAEs should be submitted within 15 working days of the Chief Investigator becoming aware of the event, using the HRA report of serious adverse event form (see HRA website).

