6. OBJECTIVES AND OUTCOME MEASURES

	Objectives	Outcome Measures			
Primary	Feasibility of recruitment and data collection.	40 patients randomised 1:1 between the standard pathway and accelerated pathway proportion of eligible patients who agree to randomisation / data completeness / availability and participant completion.			
Secondary	 Mean change and standard deviation in breathlessness 	 100mm VAS scores completed before and after the procedure and 3x weekly thereafter for 6 weeks 			
	2. Patient anxiety and depression	 Hospital anxiety and depression score (HADS) weekly for 6 weeks 			
	3. Health Related Quality of Life	3. EQLQ-C30 questionnaire, EQ 5D-5L questionnaire weekly for 6 weeks			
	4. Time to actionable histopathology /diagnosis	4. Cancer multi-disciplinary team consensus			
	5. Healthcare utilisation	5. Number of pleural procedures and days in hospital post enrolment			
	 Assess the acceptability to patients of the accelerated pathway and patient priorities 	 Perform structured qualitative interviews with a proportion of patients in both the standard care arm and accelerated arm and those declining participation. 			
	7. Proportion of adverse events for both arms	7. Record agreed adverse events			

[figure not shown]
Patient group	Patients with suspected malignant pleural disease, based on any of: presentation, imaging, prior asbestos exposure or history of malignancy:
Intervention(s)	First procedure as a pleural biopsy (local anaesthetic thoracoscopy if available or image guided biopsy if local constraints preclude thoracoscopy) AND Indwelling pleural catheter (IPC) insertion in a single procedure = the accelerated pathway
Comparator	Standard care pathway as defined by the current British Thoracic Society Guidelines, with first procedure as pleural aspiration only, followed by subsequent procedures for tissue biopsy and definitive fluid control

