7. STUDY DESIGN

STREAMLINE is a prospective, up to three centre, randomised feasibility study of patients with a new, suspected malignant pleural effusion, who will be randomly allocated to receive either the accelerated pathway or standard care pathway (based on the BTS guideline 2010).

Patients randomised to the accelerated pathway will undergo a pleural procedure, a pleural biopsy + IPC insertion at their first visit. The pleural biopsy can be performed via either ultrasound guided pleural biopsy OR local anaesthetic thoracoscopy depending on local expertise, resource availability and managing clinical team decision making.

Patients randomised to the standard care pathway will be managed according to the updated 2023 BTS guidelines, which list pleural aspiration as the index procedure, followed by assessment of pleural fluid results and cytology, and progressing to pleural biopsy, IPC or talc pleurodesis as per MDT decision making and patient choice.

We aim to recruit 40 patients Randomised 1:1 with probable MPE over an 18-month period with a 3 month follow up period. Patients will be typically recruited from their pleural clinic at each hospital in which each centre sees up to 20 patients with suspected MPE per month. The units perform an average of 12 procedures per week including 2 thoracoscopies and 2 ultrasound guided biopsies per week.

In-depth Participant Interviews

Qualitative interviews will be performed on a proportion of participants. These interviews will be performed by either the trial fellow or research nurse. Pseudonymised transcripts will be transcribed by an external transcription company. In addition, a proportion of those participants who refused randomisation but consented to be interviewed will also be approached to take part if willing, and, any themes arising from these two groups will be incorporated into the design of the subsequent definitive randomised controlled trial. The interviews will be performed either face to face, over the phone or via /audio conferencing. These recordings will be stored securely, electronically on the ORTU network drive before being sent to the transcription company. Once the transcription has is received these audio files will be deleted. Interviews will be conducted using participant ID's only, no names will be used during the interview.

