11.4. Analysis populations

The study will be analysed on intention to treat, with included populations as specified above.

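### Serious adverse events are recorded only from the first procedure, so events in the wait of up to one week after open randomisation are left out of the by-arm safety comparison

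*Protocol*

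**What the plan says.** **Start of the safety window.** Protocol section 10.3: "The safety reporting period is for 6 weeks post initial procedure", ending earlier if the IPC is removed before then. Section 10.2 limits collection: "only adverse events meeting the criteria to be a Serious Adverse Event will be recorded". Section 10.3 sends SAEs that do not need expedited reporting to the procedure, discharge or follow-up CRF. It names no form for the time before the procedure.

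**Start of the randomised comparison.** Section 9.4 says that, in every case, "randomisation can occur on the day of procedure, or up to 1 week in advance to allow for planning of procedure lists". In the section 9 schedule, the column that holds consent, baseline and randomisation carries a looser window of up to 14 days before day 0. Section 9.5: "The trial will be unblinded due to the nature of interventions".

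**What is compared.** Secondary objective 7 in section 6 is "Proportion of adverse events for both arms". Section 11.4: "The study will be analysed on intention to treat, with included populations as specified above". Section 11.1 says that no separate statistical analysis plan is in use, so these sections are the whole plan on this point.

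**The concern.** The trial compares two pathways, and a patient belongs to a pathway from allocation. The safety record begins later, at the first procedure. A serious deterioration, an admission or a death in between is experienced under the allocated pathway but is not counted as an SAE for either arm. A patient who never reaches the procedure stays in the intention-to-treat denominator and can contribute no event.

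The omission follows from a stated rule and is not a detail left open. At stake is whether objective 7 describes harm from randomisation or only harm from the procedure onwards. Serious events during the wait for the allocated first procedure also bear on whether the accelerated pathway can be delivered, which the lay summary gives as a reason for the trial.

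**Working it through.** The protocol states no figure on this point, so there is none to reproduce. The check compares the two time origins and then sizes the gap.

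**1. Uncovered share of time from randomisation to week 6**

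Inputs: safety window of 6 weeks = 42 days (section 10.3, taking no early IPC removal); wait *w* of 0 to 7 days (section 9.4), or up to 14 days if the schedule's column applied to randomisation.

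Formula: *w* / (*w* + 42).

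| Wait *w* | Calculation | Uncovered |
|---|---|---|
| 0 days | 0/42 | 0% |
| 3 days | 3/45 | 6.7% |
| 7 days (section 9.4 maximum) | 7/49 | 14.3% |
| 14 days (schedule column) | 14/56 | 25% |

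**2. Patients with an unrecorded SAE**

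Inputs: 20 patients per arm (40 randomised 1:1, section 6). The protocol gives no SAE rate, so weekly risks *r* of 2%, 5% and 10% are assumptions that show a range.

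Formula: 20 × [1 − (1 − *r*)^(*w*/7)]. At *w* = 7 this is 20 × *r*.

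| Assumed weekly risk | Per arm, 7-day wait | Shift in the difference, waits 7 v 0 days | Waits 7 v 2 days | Equal waits |
|---|---|---|---|---|
| 2% | 0.4 | 2 points | 1.4 points | 0 |
| 5% | 1.0 | 5 points | 3.5 points | 0 |
| 10% | 2.0 | 10 points | 7.0 points | 0 |

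The shifts are percentage points in the proportion of patients with an event missed, and favour whichever arm waits longer. For a given risk and pair of waits they are at most this large in the reported proportions, because a patient with an SAE in the gap may have another that is recorded later.

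**3. Other routes by which the events might be captured**

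- Section 6 counts days in hospital from enrolment, under healthcare utilisation.
- Section 9.8 collects admissions for any cause at follow-up visits.
- Section 11.2 lists all-cause mortality by record review, with no stated start.
- The adverse-event row of the schedule appears to start on the day of procedure. The table is broken in the text available, so this reading is probable and not certain.

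The first three may catch admissions and deaths in the gap. None of them places these events in objective 7, and nothing says that they reach the Safety Oversight Group, which under section 13.3 reviews reported SAEs.

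**The case against.** **Events before the procedure cannot be caused by it, and all the interventions are standard practice, so starting at the procedure is defensible.** This holds for expedited reporting, which section 10.3 ties to the study procedure. It does not hold for recording: the same section has SAEs judged unrelated entered on the CRFs. Relatedness decides how fast an event is reported, not whether it is counted.

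**Intention to treat fixes who is analysed and in which arm, not when collection starts.** This is correct. The two sections do not formally contradict each other. The point is that the safety comparison starts from a different origin from the randomised comparison.

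**Admission and death are the main SAE criteria and are partly captured elsewhere.** This stands, and it reduces the loss to the SAE comparison itself, plus serious deterioration without admission.

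**The consequence is small.** This also stands. It is a 40-patient feasibility study, section 11.7 sets no significance level, and none of the five progression criteria in section 11.2 uses adverse events.

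**Two stronger readings that the documents do not support**

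- *The omission falls mainly on the accelerated arm.* A reader might infer this from section 7: "The units perform an average of 12 procedures per week including 2 thoracoscopies and 2 ultrasound guided biopsies per week". However, section 9.4 applies one rule to both arms, and no waits by arm are given. A count of procedures performed does not show scarcity: 4 biopsy procedures a week is about 17 a month (4 × 52/12), whereas 20 accelerated-arm patients over 18 months is about 1.1 a month, although other patients use those slots too.
- *The pilot data in section 5 give the event rate.* A reader might spread the 60% who made an emergency call or were admitted over the roughly 70-day pathway. Section 5 gives no period for that 60%. It comes from 17 patients, includes calls that need not be SAEs, and describes patients who had mostly had repeated procedures, not patients waiting for a first one. It supports neither an estimate nor an upper bound for the gap.

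**Conclusion.** The point holds as a gap in coverage of modest consequence. SAEs between randomisation and the first procedure are outside the by-arm comparison by rule, and a patient who dies or withdraws in that time has no safety window. The size is 14% of the time from randomisation to week 6 for a patient who waits the full week, and about zero for one randomised on the day. In patients, it is about 0.4 to 2.0 per arm if everyone waits a week, under assumed weekly SAE risks of 2% to 10%.

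Bias in the difference is conditional. It needs waits that differ by arm, which is plausible because one arm needs biopsy and IPC in a single procedure, but is not shown anywhere in the protocol. With equal waits and similar risks, events are lost from both arms and the difference is little affected.

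**What to change.** 1. In section 10.3 and the schedule, start SAE recording at randomisation in both arms. The expedited-reporting rule can stay as it is. State what end of recording applies to a participant who never has a first procedure, since the present end is counted from that procedure.
2. For objective 7, count the by-arm total from randomisation, and show events before and after the first procedure separately.
3. Record days from randomisation to first procedure and report them by arm. This shows whether waits differed and is useful feasibility information for a definitive trial.
4. Reconcile the one-week limit in section 9.4 with the 14-day column in the schedule that includes randomisation.

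Cost: a wording change, one extra CRF item on the day of procedure, and a few more events recorded.
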